1.0 Objectives

In this multistep study, we will build on our prior efforts¹ to develop consensus on surveillance mammography and follow-up for breast cancer survivors who are age ≥ 75 by further developing expert-panel recommendations, examining clinician and patient attitudes towards these recommendations, and testing a strategy for communication of expert recommendations on mammography cessation through direct engagement of specialists, primary care clinicians (PCs), and patients. Specifically, we will work to reduce overscreening of older patients through the following aims:

- 1.1 Develop a communication tool that summarizes recommendations for clinicians and patients for surveillance mammography and follow-up care for breast cancer survivors age ≥ 75 . This will build off the work of a multidisciplinary expert panel which will come together for a meeting to develop draft recommendations (OHRS exempt protocol #18-526).
 - Interview up to 30 patients through telephone-based patient interviews and focus groups and interview oncologists and primary care providers (PCs) through 4-6 focus groups to learn their perceptions and thoughts about when to stop surveillance mammography, how to thoughtfully incorporate life expectancy into decision-making, how to communicate the benefits/risks of surveillance mammography, obtain feedback on the communication tool, and to explore optimal strategies for integrated and unified care between disciplines
 - Perform cognitive testing of the communication tool in up to 10 Dana-Farber breast cancer patients and further refine it for Aim 1.2
- 1.2 Test the surveillance mammography communication tool with older breast cancer survivors and their oncology clinicians
 - In a pre-post intervention study, examine the effect of the communication tool among 45 breast cancer survivors age ≥ 75 years (with low risk of in-breast recurrences) seen by oncologists on women's intentions for and knowledge of the pros and cons of surveillance mammography.

We hypothesize that our communication tool will lead to fewer women intending to receive surveillance mammography in the next year and women having more knowledge of the benefits and risks of surveillance mammography.

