
- 5.2 Procedures for recruiting focus groups - Providers (Aim 1.1). [name] will email her colleagues at Brigham and Women's and DFCI to recruit them for a 60- minute focus group discussion, aimed to occur at a regular weekly/monthly meeting for a particular PCP or medical oncology practice. We will provide beverages and snacks for the meeting. We will visit the practice at BWH or DFCI to conduct the focus groups and any virtual focus groups will take place by phone via webex. [name] will also reach out to her broad network of physicians outside of DFCI to recruit oncologists from around the country for the virtual focus group (which will occur via

PROTOCOL TITLE:

webex/phone). [name] (who is experienced in leading clinician-based focus groups) will lead all clinician focus groups. All discussions will be recorded and professionally transcribed. At the start of the clinician focus groups, verbal consent from each participant will be obtained and providers will be provided a written copy of the verbal consent in person or via email. We do not intend to register providers in Oncpro.

- 5.3 Procedures for recruiting providers and patients for the tool intervention (Aim 1.2)
We will then test the communication tool at DFCI, DFCI at South Shore Hospital , and DFCI at St. Elizabeth's breast medical oncology practices. [name] will recruit 10-12 medical oncology colleagues who each agree to test the communication tool in ≤5 of their older patients over a 4-6-week period.

Before the visit. To identify mammography-eligible patients with low-to-average risk for in-breast recurrences, the dedicated CRC will scan participating clinician schedules daily over a 4-6-week period at DFCI/St. E's/South Shore Hospital for breast cancer patients with stage 0-II breast cancer who have completed any chemotherapy, surgery, and/or radiation ≥12 months prior and who are aged ≥75 and who had breast-conserving surgery. If a patient meets criteria for possible enrollment, the CRC will email the clinician (Appendix H) to confirm that mammography would typically be discussed at this visit and to ask permission to offer the study to the patient.

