If the clinician agrees, the CRC will send information and what will be used for verbal consent (Appendix F) to the patient with an opt-out number and email followed by a phone call (to those who do not opt out) to explain the study's purpose and obtain verbal consent for participation. The CRC will share a blank communication tool to the patient with the 'pre'survey to be filled out before the visit (clinic visit can be virtual or in person), and notify the clinician when a patient enrolls. This can be sent to the patient by mail or email in advance of their virtual/in person clinic visit. If the patient prefers the materials to be given to them in person, the CRC will arrange to meet the patient 30 minutes before their scheduled clinic visit. If the clinic visit is virtual, the CRC can call the patient anytime ahead of the provider visit to review the materials. The study team will be utilizing standard clinical workflows and may involve virtual substitution of office visits such as the use of Zoom Video Communications application. Although in-person office visits are preferred on site, virtual visits via Zoom conferences, which are HIPPA compliant and protected, can provide a safer and efficient alternative for patients.

Visit Day. The day before the clinic visit (virtual or in-person), the CRC will call or email the patient to remind them to fill out the 'pre'-survey and send it to the study team. We will also remind the clinician that the patient is coming/being seen virtually and will email or hand-deliver a blank communication tool before the visit so they are aware it may be discussed. The CRC may meet the patient in the waiting room or communicate by phone/email before their appointment to collect the 'pre' survey (if not already received via email/mail) A copy of the verbal consent can also be given in person or via email/mail if not already done ahead of this visit. Clinicians will be reminded to incorporate the communication tool in a way that feels comfortable to them to facilitate routine practice but without specific instructions. After the visit, the CRC

PROTOCOL TITLE:

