****Post-visit Clinician Questionnaire****

Thank you for agreeing to participate in this study. We are going to ask you some questions relating to this particular visit with the patient. All of your answers will be kept confidential, will not be linked to your name for future use, and are for informational purposes only as we try to understand how helpful this tool was in your discussions with patients. Please answer openly and honestly and you can skip any question you prefer not to answer

Study ID _____

Date: _____

Intentions for mammography

1. What did you recommend in terms of mammograms for this patient?

- Continue having mammograms
- Get another mammogram but consider stopping after that
- It is the patient's choice
- To not get a mammogram now but reconsider later
- To stop getting mammograms
- Did not discuss mammograms
- Other: _____

2. Before the visit, what did you think you would recommend?

- Continue having mammograms
- Get another mammogram but consider stopping after that
- It is the patient's choice
- To not get a mammogram now but reconsider later
- To stop getting mammograms
- I did not think I would discuss mammograms
- Other: _____

3. During the visit today, did you discuss any of the following (circle each answer):

- | | | | |
|--|-----|----|----------|
| • Pros of mammograms? | Yes | No | Not sure |
| • Cons of mammograms? | Yes | No | Not sure |
| • The patients individual risk of in-breast, pre-cancer or invasive cancer events? | Yes | No | Not sure |
| • Family history? | Yes | No | Not sure |
| • Life expectancy? | Yes | No | Not sure |

PROTOCOL TITLE:

- Any other relevant discussion points you discussed?
-

3A. If yes to discussing life expectancy, how did this go? Check any that apply:

- Helpful to patient
- Helpful to me
- It was uncomfortable
- It was comfortable
- Made decision-making easier for mammogram
- Made decision-making harder for mammogram
- Neutral effect on decision-making
- Other _____

3B. If no to discussing life expectancy above, why not? Check any that apply

- It didn't come up
- I was uncomfortable talking about it
- Patient did not want to discuss it
- Patient was anxious
- Patient healthy so I didn't think it was important
- I didn't have time
- I didn't think it was important for this discussion

Questions about the Communication Sheet (with regard to its use during this visit with the patient)

4. The length of the communication sheet was

- | | | | | | |

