|--------------------------|--------------------------|--------------------------|--------------------------|--------------------------|--------------------------|
|  |  |  |  |  |  |
| Much too Long | A little too long | Just right | A little too short | Much too short | I didn't use it |

5. The amount of information was

- | | | | | | |
|--------------------------|---------------------------|--------------------------|---------------------------|--------------------------|--------------------------|
|  |  |  |  |  |  |
| Much less than needed | A little less than needed | Just right | A little more than needed | Much more than needed | I didn't use it |

6. How clear was the information?

- | | | | | |
|--------------------------|--------------------------|--------------------------|--------------------------|--------------------------|
|  |  |  |  |  |
| Everything was clear | Most things were clear | Some things were clear | Many things were unclear | I didn't use it |

PROTOCOL TITLE:

7. I found the information

- | | | | | | |
|---|--|--------------------------|--|---|--------------------------|
|  |  |  |  |  |  |
| Clearly slanted
towards getting
a mammogram | A little slanted
towards getting
a mammogram | Completely
balanced | A little slanted
towards NOT
getting a mammogram | Clearly slanted
towards NOT
getting mammogram | I didn't
use it |

8. How helpful was the communication tool in making a decision about mammography?

- | | | | | | |
|--------------------------|--------------------------|--------------------------|--------------------------|--------------------------|--------------------------|
|  |  |  |  |  |  |
| Very helpful | Somewhat helpful | A little helpful | Not helpful | I didn't
use it | |

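### Aim 1.2's pre-post change in mammography intention combines the tool with an oncology visit, so it cannot be reported as the effect of the tool

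*Protocol*

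**What the plan says.** **The claim.** Protocol section 1.0 (Aim 1.2) states: "In a pre-post intervention study, examine the effect of the communication tool among 45 breast cancer survivors age ≥ 75 years". The hypothesis is causal: "We hypothesize that our communication tool will lead to fewer women intending to receive surveillance mammography in the next year". The last paragraph of section 8.5 says the study will yield preliminary data on the tool's impact on care.

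**The interval.** Under section 5.3 the pre-survey is completed before the clinic visit and the post-survey up to 7 days after it. Before enrolment the coordinator is to email the clinician "to confirm that mammography would typically be discussed at this visit".

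**Use of the tool.** Clinicians are reminded to "incorporate the communication tool in a way that feels comfortable to them to facilitate routine practice but without specific instructions". In Appendix D, clinician items 4 to 8 each offer a response for not having used the tool. Clinician item 2 asks: "Before the visit, what did you think you would recommend". Patient post-visit item 41 asks whether mammography was talked about.

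**The analysis.** Sections 8.4 and 8.5 compare pre with post within patients, using a signed-rank test on the 1-15 score and an exact McNemar test on the proportion answering yes. Random effects or a bootstrap handle clustering by clinician. There is no comparator and no analysis of change by visit content or tool use. The SAP names no test of intention; its only pre-post test is a t-test on decisional conflict.

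**The concern.** Two things happen to each woman between the measurements: she receives the tool, and she has a consultation at which her oncologist is expected to raise the same decision. A woman whose clinician already meant to advise stopping, and who never opened the tool, gives the same shift as a woman persuaded by it. A woman moved by the tool and then reassured into continuing gives no shift.

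This does not depend on the order of tool and baseline. Section 5.3 says "The CRC will share a blank communication tool to the patient with the 'pre'survey to be filled out before the visit", which raises its own question about whether the baseline precedes the tool. Even if every baseline were completed first, the consultation would still lie inside the interval.

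At stake are the wording of the conclusion on a primary outcome and the number carried forward. Section 2.7 presents the study as preparation for a randomised study. If the control arm there has a usual visit, the relevant contrast is tool plus visit against visit alone, which Aim 1.2 does not estimate.

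**Working it through.** The plan gives no figure to reproduce. For Aim 1.2 it states 45 patients without alpha, power, effect size or SD, and the sample-size reasoning in section 8.2 concerns Aim 1.1 only. The figures below illustrate scale; two-sided alpha of 0.05 is assumed throughout.

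**1. Identification.** For each woman, observed change = tool effect + visit effect + retest or time effect. One group measured twice gives one equation with three unknowns. More patients make the sum more precise but do not separate its parts.

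**2. How few movers give significance.** The protocol's yes category is scores 1-5. Exact McNemar with k women leaving yes and none entering it gives p = 2 × (1/2)^k.
- k = 5: p = 0.0625
- k = 6: p = 0.03125, and 6/45 = 13.3%

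Section 5.3 plans 10-12 clinicians with at most 5 patients each. Two clinicians could have at most 10 enrolled women, so 6 of 10 (60%) would be enough. At the average load of 45/12 = 3.75 to 45/10 = 4.5 per clinician, two clinicians see 7.5 to 9 women, and 67% to 80% of these would have to move while nobody else did. This is possible but demanding.

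**3. Rejection rate with a tool effect of exactly zero.** The visit-only shift is assumed, in SDs of the change score, with 45 pairs. The signed-rank column comes from 4,000 simulated studies with normal changes; the paired t column comes from the noncentral t distribution.

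| Visit-only shift | Signed-rank rejects | Paired t rejects |
|---|---|---|
| 0 | 5% | 5% |
| 0.2 | 25% | 26% |
| 0.3 | 49% | 50% |
| 0.4 | 73% | 75% |
| 0.5 | 90% | 91% |

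For exact McNemar, assume the visit alone moves 2% of women into yes and 10%, 15% or 20% out of it. The test then rejects in about 15%, 44% and 70% of studies.

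**4. The opposite direction.** If the tool moves intention by +0.4 SD and the visit by -0.4 SD, the net shift is 0 and the first row of the table applies: a real tool effect would be found about 5% of the time.

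**5. Consequence for the next study.** If a fraction f of the pre-post change is due to the tool and the SD is unchanged, the sample size needed scales as 1/f². For f = 0.75, 0.5 and 0.25 the multiples are 1.8, 4 and 16. A trial planned on the full change when half of it came from the visit would have one quarter of the patients it needs.

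**The case against.** **It is a declared pilot.** Section 2.7 and the SAP both say the results feed a later trial, section 8.5 calls them preliminary, and most of 8.4-8.5 describes the outcome neutrally as a change in intention. This limits the consequence. It does not remove the causal wording in the objective, the hypothesis and the end of 8.5, and planning a trial is where the wrong contrast does harm.

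**The tool is meant for the consultation.** Its fourth section is about deciding with the doctor, so tool plus visit could be called the intervention. That is reasonable, but the comparison is then a visit without the tool, which is not observed.

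**Clustering is handled.** Random effects or a bootstrap would widen the interval if the change came from a few clinicians. They do not attribute the change to the tool.

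**Stronger readings that do not stand.**
- A reader might infer that visits are selected because mammography will be discussed. They are found by scanning schedules for age, stage, surgery and time since treatment; the clinician's confirmation is a further check. It is not among the section 3.4 criteria, and the Appendix H email neither asks the question nor requires a reply. Some visits may contain no such discussion.
- A reader might infer that the visit must inflate the result. Section 2.2 says clinicians find cessation hard to discuss and that widely cited guidelines still favour annual mammography. Section 2.6 reports that 57% of survivors with a life expectancy of 5 years or less had a mammogram in the last year. Usual visits may well reinforce mammography.
- A reader might take clinician item 2 as a prospective record. It is recalled on a post-visit form, which section 5.3 places after all of that clinician's participating patients have been seen.

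**Conclusion.** The point holds as one of attribution. The Aim 1.2 pre-post change measures tool plus visit plus retest. It cannot support a statement about the effect of the tool or its impact on care.

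The size of the distortion cannot be stated, because the documents give no figure for how usual visits change intention. It may inflate or mask a tool effect. The rejection rates in the working rest on assumed shifts and an assumed alpha; they show that modest visit effects would matter at 45 patients, not that they occur. Nothing here shows that the tool has no effect.

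Acceptability and feasibility, the other primary outcome, is unaffected. Nor does the point require a control arm in this pilot: 45 patients split 22/23 would have about 29% power for 0.42 SD, the shift that 45 pairs detect with 80% power.

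**What to change.** 1. **Reword.** In section 1.0 (objective and hypothesis) and the close of 8.5, describe the result as *change in intention across a tool-supported visit*. State as a limitation that tool, visit and retest effects are not separated and that the visit could act in either direction. Do not use the pre-post change as the tool-versus-usual-visit effect when sizing the randomised study.
2. **Describe the change by visit content.** From items already collected, report the pre-post change by whether mammography was discussed (patient item 41), whether the clinician used the tool (clinician items 4-8) and the clinician's recalled plan (clinician item 2). The SAP already describes clinician recommendations and discussion per patient; the addition is to relate them to change in intention. Label these splits as post-baseline and non-random and, for item 2, retrospective. They do not identify the tool effect. A clinician's not using the tool also does not mean that the woman did not read it.
3. **Optional, if data are still being collected.** Repeat the intention item after the woman has read the tool and before the visit. This is interpretable only if the pre-survey is completed before the tool is seen. The day-before contact cannot be relied on for it, since that contact reminds women to complete the pre-survey. The repeat would measure reading the tool, not its use in the consultation, and some women may simply give their earlier number again. The SAP is written in the past tense, so this may apply only to a later study.

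Items 1 and 2 cost wording and three small tables, with no new data. Item 3 would need a changed survey sequence as well as one question.

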- Previous diagnosis of stage 0-II breast cancer
- Receive some/all care at Dana-Farber Cancer Institute and affiliated satellite sites (Boston's main campus, South Shore Hospital, or St. Elizabeth's Medical Center)
- Completed any active breast cancer therapy ≥ 12 months prior to enrollment (i.e. any chemotherapy, trastuzumab, radiation). Ongoing hormonal therapy or enrollment in survivorship clinical trials (aspirin, exercise, etc) is allowed.
- Age ≥ 75
- Had breast-conserving surgery to treat this cancer
- Provider does not opt out of the patient's enrollment via email notification
- English speaking and reading

For all study aims, we will exclude patients who:

- are unable to consent
- who do not read and write English (for this initial pilot)

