- 8.4 Outcomes and Analyses for Aim 1.2. The outcomes of interest are shown in Table 2 below and have been adapted from [name] prior survey study testing a decision aid for screening mammography for older women.⁶⁶ We will focus on a primary outcome of intentions for mammography and will examine how various factors (race, health literacy, numeracy, anxiety, life expectancy) impact intentions. We use the sign rank and exact McNemar’s testing to compare the ‘pre’ vs. ‘post’ results for the continuous score for intention and proportion who indicate ‘yes’, respectively. To account for clustering by clinician, we will utilize random effects models if parametric assumptions hold, or alternatively using bootstrap resampling techniques to compute 95% confidence intervals for the change in intention. We anticipate a low number of missed surveys because of the CRC follow-up planned by phone, mail, or email if necessary. If a patient is missed for her ‘pre’ test survey, we will replace her to ensure enrollment of 45 with ‘pre’ and ‘post’ surveys. We will compare characteristics of those with missing surveys and missing questions to those with complete surveys to assess for any notable differences.

Table 2. Outcomes of Interest for Aim 1.2	
Outcome(s) of Interest	Outcome definitions, planned analyses

PROTOCOL TITLE:

Primary Outcomes: Patients: Frequency of change in intentions for mammography in the next year	15 point validated scale to assess ‘pre’ vs ‘post’ survey responses where scores 1-5 = yes to having mammography, 6-10 = unsure, 11-15 = no for mammography. We will use a continuous outcome of 1-15. ^{66,79}
Patients & Clinicians: Acceptability & Feasibility	Length, clarity; tabulate responses ⁸⁰ ; 75% report the tool is useful
Secondary Outcomes:	
Clinicians: satisfaction, time added/removed	Tabulate responses, prepare descriptive analyses
Patients: preferred decision-making role	‘Pre’ survey: Examine preferences for active, shared, passive decision-making ⁸¹
Patients: Decisional conflict	‘Pre’ vs. ‘Post’ survey: 16 item scale, Calculate total and sub-scale responses. Scores range 1-100, lower scores indicating higher quality decision-making ^{82,83}
Patients: Knowledge about mammography	Number of correct (10) knowledge questions on ‘pre’ vs. ‘post’ surveys. ^{66,84,85}

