24.0 Provisions to Protect the Privacy Interests of Subjects

Study staff will obtain permission from the primary medical oncologist before contacting potential subjects. Only study staff who have completed institutional training and are familiar with the protocol will contact patients for an informed verbal consent. Only staff who have completed training can access Epic or other patient medical record databases. Study staff may conduct a limited review of a patient's medical record in order to confirm eligibility; they may continue to access their records.

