Per our medical record review, it seems that *[name] is aged 75 or older, had breast conservation, and is in long-term follow-up care for her breast cancer. She is likely eligible for protocol 19-001.* As you may know, this is survey-based study where patients will be given an information tool to discuss mammography with you that can be used as you like and per your discretion. Patients will be surveyed before and after your visit on their mammography decisions and how the information tool may have helped/not helped them make decisions. Participants will receive \$40 for their time. ***This cohort is purely survey-based and there is no therapeutic component to the study.***

If we do not hear from you within 2 business days, we will assume permission to initiate contact with the patient. We will mail your patient an introduction to the study and then call them a week later to assess their interest. If this patient is interested in participating, we will be responsible for consenting her and for all study procedures. **We will survey you at the end of the patient encounter via email and at the end of the study, you will receive a \$40 amazon gift card in appreciation of your time.**

Thank you for your assistance and support of this study. Please feel free to contact us if you have any questions.

Sincerely,

[name], MPH

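### The clinician email that Section 5.3 relies on to confirm a mammography discussion never asks about one, and the rules on clinician permission conflict

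*Protocol*

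**What the plan says.** Protocol Section 5.3 describes enrolment for the Aim 1.2 pilot. The coordinator scans clinic schedules for women who meet the age, stage, surgery and time-since-treatment criteria. The coordinator then emails the clinician "to confirm that mammography would typically be discussed at this visit and to ask permission to offer the study to the patient". The next step depends on the answer: "If the clinician agrees, the CRC will send information".

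The email is drafted in Appendix H. It gives the patient's age group, says that she had breast conservation, and says that she "is in long-term follow-up care for her breast cancer". On the study it says that "patients will be given an information tool to discuss mammography with you that can be used as you like and per your discretion". On permission it says: "If we do not hear from you within 2 business days, we will assume permission to initiate contact with the patient".

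Two other places deal with permission. An eligibility criterion in Section 3.4 reads "Provider does not opt out of the patient's enrollment via email notification". Section 24.0 reads "Study staff will obtain permission from the primary medical oncologist before contacting potential subjects".

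On the analysis, Section 8.4 says "We will focus on a primary outcome of intentions for mammography". It compares scores before and after the visit in 45 women with both surveys. Section 8.5 repeats the comparison and adds acceptability and feasibility as primary outcomes.

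**The concern.** Section 5.3 uses the email as its check that the coming visit is one at which mammography would ordinarily be raised. The email as drafted contains no such question. Even if it did, a clinician who does not reply has confirmed nothing, and the email lets recruitment go ahead in that case. A coordinator who follows Appendix H to the letter therefore skips a check that Section 5.3 says is made.

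Two things are at stake. First, the intervention is a tool plus a conversation. Women whose visit has no conversation receive only part of it but count fully in the pre-post change, which could make the change smaller than it would be in the visits the protocol meant to enrol. Second, staff cannot tell from the protocol whether silence allows them to contact a patient. That is a privacy question and needs one answer, whatever its effect on the estimate.

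**Working it through.** **Step 1. Is the check made anywhere?**

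| Place | Deals with a mammography discussion at this visit? |
|---|---|
| Section 3.4, eligibility | No such criterion |
| Section 5.3, schedule scan | No; covers age, stage, surgery and treatment timing |
| Section 5.3, purpose of the email | Yes; assigns the check to the email |
| Appendix H, the email | No question; describes the tool and the patient's history |
| Appendix D, clinician items 1 and 2 | Recorded, but only after the visit |
| Appendix D, patient item 41 | Recorded, but only after the visit |

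The check is assigned once and carried out nowhere before enrolment.

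**Step 2. Is permission consistent?**

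| Place | A clinician who does not reply |
|---|---|
| Section 5.3 | Has not agreed, so no contact |
| Section 24.0 | Permission not obtained, so no contact |
| Section 3.4 | Has not opted out, so eligible |
| Appendix H | Permission assumed after two business days |

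The split is two against two.

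**Step 3. Does the analysis deal with such visits?** Sections 8.4 and 8.5 name no exclusion, subgroup or sensitivity analysis for them. The SAP describes clinician answers patient by patient, but does not use them to define who is analysed. Yet the surveys foresee these visits. Clinician item 1 has an option for not having discussed mammograms, item 2 has one for not having expected to, several clinician items have one for not having used the tool, and patient item 41 asks directly whether mammography was discussed.

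**Step 4. How large could the effect be?** There is no figure in the plan to reproduce: for Aim 1.2 the documents give no effect size, standard deviation, alpha or power, and no rate of visits without discussion. What follows is an illustration only. Assume that a share d of visits has no discussion, that those women do not change at all, and that the standard deviation of change is unaffected. The mean change is then multiplied by (1 − d), and the information is that of 45 × (1 − d)² women. If the design had 80% power at two-sided 0.05 with d = 0 (also an assumption), power becomes Φ((1 − d)(1.960 + 0.842) − 1.960).

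| d (assumed) | Mean change multiplied by | Equivalent n | Power |
|---|---|---|---|
| 0% | 1.0 | 45 | 80% |
| 10% | 0.9 | 45 × 0.81 = 36.5 | 71% |
| 20% | 0.8 | 45 × 0.64 = 28.8 | 61% |
| 30% | 0.7 | 45 × 0.49 = 22.1 | 50% |

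If reading the tool alone lowers intention, the dilution is smaller than shown. Section 5.3 sends the tool together with the pre-visit survey and does not fix which is read first, so the documents cannot settle how much change the visit itself contributes.

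**The case against.** A reader might infer that the tool is irrelevant at a visit without discussion, so that such women do not belong in the analysis. The documents do not support that. Each woman receives the tool before her visit. Most of it is for her own use (risk charts, a health score, a list of reasons for and against), and the outcome is her own intention for the next year. Entry requires breast-conserving surgery, so mammography is a live question for her whether or not the clinician raises it.

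A reader might also infer that Appendix H departs from the rest of the protocol on permission. It does not: Section 3.4 is opt-out too.

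Other steps make undiscussed visits less likely. Participating clinicians agree beforehand to test the tool. The email tells them that it is for discussing mammography, so they can decline a patient. They are also told of each enrolment and reminded before the visit. The design is pragmatic: clinicians use the tool as they find comfortable, and the criteria were chosen for generalizability. On that view, some visits without discussion are part of real use, and keeping them in the estimate is defensible. Appendix H is also labelled a draft.

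All of this stands, and it limits the consequence. It does not remove the gap. None of these steps confirms anything about a particular visit, and Section 5.3 itself says that this confirmation is sought. A draft that is the only text carrying out Section 5.3 should carry it out.

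Finally, a reader might want the main analysis limited to women who answer yes to patient item 41. That would select on something that happens after the tool is given and that the tool is meant to prompt. Those women may differ in motivation, and the restricted estimate could overstate the effect.

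**Conclusion.** The point holds as a mismatch between Section 5.3 and Appendix H, with a separate conflict over permission among Sections 3.4, 5.3, 24.0 and Appendix H. Followed as drafted, the email does not make the visit check, and visits without a mammography discussion can be among the 45. Both findings rest on the text alone.

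The size of any dilution is unknown. The figures in the table depend on an assumed share and on zero change without discussion, and the documents support neither. They should not be read as an estimate of lost power, nor as a reason to call the primary analysis invalid. The change is still worth making before enrolment: it is nearly free, and it brings enrolment into line with what the protocol says it intends.

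**What to change.** 1. Add one yes/no line to the Appendix H email asking whether the clinician would ordinarily raise mammography at this appointment. Record the reply, and do not invite the patient if the answer is no. If the check is not wanted, remove that purpose from Section 5.3 instead.
2. Reconcile Sections 3.4, 5.3, 24.0 and Appendix H on whether a non-reply permits contact. If it does, log those visits as unconfirmed so that they can be counted.
3. Keep all enrolled women in the primary analysis of intention.
4. Report descriptively, from items already collected, how many visits had no mammography discussion or no tool use: clinician items 1 and 2, the clinician options for not having used the tool, and patient item 41.
5. Label any analysis restricted on item 41 as exploratory, and give the reason.

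The cost is one line in an email, a reminder to clinicians who do not answer, and slightly slower accrual. No new data collection is needed beyond logging the reply.
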